2.2. Success criterion

The study will be determined as successful if it satisfies two conditions:

- 1. The difference in the change of TBUT, between eyes in the study arm and eyes in the control arm, is statistically significant at the α = 0.05 level.
- 2. The *change* of TBUT is *higher* in eyes of the study arm, compared to eyes of the control arm

where the *change* of TBUT is defined as TBUT at the follow-up minus TBUT at the baseline.

- **2.3.** Secondary efficiency endpoints
 - The difference in the *change* of OSDI, between subjects in the study arm and subjects in the control arm
 - The difference in the *change* of EDS, between subjects in the study arm and subjects in the control arm

where the *change* of the variable (OSDI or EDS) is defined as the value of the variable at the follow-up minus the value of the variable at the baseline.

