4.1. Effectiveness

4.1.1. Primary effectiveness endpoint

The primary efficiency endpoint will be estimated as the difference in the *change* of TBUT from baseline to follow-up (10 weeks) between the study arm and the control arm, where the change of TBUT is defined as TBUT at the follow-up minus TBUT at the baseline.

A linear mixed-effect (LME) model will be used to test the null hypothesis that the changes of TBUT are not different between the two arms. The success criterion will include the following two conditions:

- 1. Two-sided p-value < 0.05
- 2. The change of TBUT in eyes of the study arm is *larger* than the change of TBUT in eyes of the control arm

The linear mixed-effect model will include a random effect for subjects to account for correlation between eyes within subjects.

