4.1.2. Secondary effectiveness endpoints

The following secondary efficiency endpoints will be estimated:

- The difference in the *change* of EDS, between subjects in the study arm and subjects in the control arm
- The difference in the *change* of OSDI, between subjects in the study arm and subjects in the control arm

where *change* is defined as the value of the variable (OSDI or EDS) at the follow-up minus the value of the variable at the baseline.

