5.2. Secondary Study Hypotheses

 The change of OSDI (△OSDI) in subjects of the study arm is *more negative* than △OSDI in subjects of the control arm, where △OSDI is defined as OSDI at the follow-up minus OSDI at the baseline:

H0: $\triangle OSDI_S \ge \triangle OSDI_C$

H1: $\triangle OSDI_S < \triangle OSDI_C$

 The change of EDS (△EDS) in subjects of the study arm is *more negative* than △EDS in subjects of the control arm, where △EDS is defined as EDS at the follow-up minus EDS at the baseline:

> H0: $\triangle EDS_{S} \ge \triangle EDS_{C}$ H1: $\triangle EDS_{S} < \triangle EDS_{C}$

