5.7. Effectiveness analyses

The primary efficacy outcome measure (TBUT) consist of a pre-treatment measurement (the baseline), a treatment intervention, and a post-treatment measurement (the follow-up). Both eyes will be included in the analysis. Since the two eyes of a subject are not independent, to estimate whether TBUT has improved from the baseline to the follow-up, a linear mixed effects model with random intercept, using the subject identity as the random effect, is the appropriate test. Since there are two eyes per person then there is only one possible covariance structure (i.e. symmetric, with a single correlation between eyes).

The secondary efficacy outcome measures are OSDI and EDS which will be collected at the baseline, and at a follow-up visit. In the case of OSDI, the value is estimated per subject. Hence, a single value will be collected per subject at each of these two visits. In this case a paired t-test is the appropriate statistical test to estimate whether dry eye symptoms have improved, using the change of OSDI from baseline to the follow-up. In the case of EDS, the value is estimated per eye. Hence, two values will be collected per subject at each of these two visits. Since the two eyes of a subject are not independent, to estimate whether EDS has improved from the baseline to the follow-up, a linear mixed effects model with random intercept, using the subject identity as the random effect, is the appropriate test. The level of

statistical significance is $\alpha = 0.05$. Non-parametric tests will be performed if the underlying distributions are not normal.

For all other eye-level analyses, where appropriate, sample means of continuous variables will be analyzed with linear mixed effects model with random intercept (whenever both eyes of a subject are included in the analysis), or two-sample t-tests. Proportions will be analyzed with χ^2 tests.

All statistical tests will be two-sided because potentially the treatment procedure may worsen the outcome. The level of statistical significance (type I error) is $\alpha = 0.05$. Non-parametric tests will be performed if the underlying distribution is not normal.

For descriptive statistics, the N, Mean, Median, Standard deviation, Standard error of the mean, 95% confidence interval, Minimum, and Maximum will be reported for continuous variables; the frequency and proportion for each category will be reported for nominal and categorical variables.

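### OSDI and EDS are each tested at two-sided 0.05 with no order, gate or adjustment, so the chance of a false symptom-benefit claim is about 4–5% rather than 2.5%

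*SAP*

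**What the plan says.** SAP 5.2, headed "Secondary Study Hypotheses", writes a null and a one-directional alternative for OSDI and another pair for EDS; in both, IPL lowers the score more than sham. Protocol 7.2 is the same.

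SAP 5.7 names the two endpoints together: "The secondary efficacy outcome measures are OSDI and EDS which will be collected at the baseline, and at a follow-up visit". It sets 0.05 for them, and then sets the rule for every analysis: "All statistical tests will be two-sided because potentially the treatment procedure may worsen the outcome", and "The level of statistical significance (type I error) is" 0.05. Protocol 7.4 carries the same text.

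Study success is defined in SAP 2.2 ("The study will be determined as successful if it satisfies two conditions") and SAP 4.1.1 ("Two-sided p-value < 0.05", plus the right direction). Both refer to TBUT alone. Neither makes the symptom tests conditional on TBUT.

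No section gives an alpha split, a sequence or a multiplicity method, and none labels the secondary endpoints supportive or descriptive. The lists do not imply a ranking either: SAP 2.3 and 5.2 put OSDI first, while SAP 4.1.2 and Protocol 6.1.2 put EDS first.

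**The concern.** The study title and Protocol 2.3 are about signs and symptoms. TBUT can support only the sign, so any symptom claim has to come from OSDI or EDS. With two formal hypotheses, each at the full level and with no link between them, a reader of the results could treat either one as establishing symptom benefit, and could lead with whichever is significant. Nothing in the plan rules this out, even when TBUT has failed. The error rate of that either-or claim is higher than the rate of one test, and the plan neither states it nor limits it.

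**Working it through.** **Inputs.** Level 0.05, two-sided, per test (SAP 5.7). Two secondary endpoints, each with an alternative favouring IPL (SAP 5.2). The documents give no correlation between the OSDI and EDS test statistics, so a range is shown.

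**The plan's own figure.** No familywise rate is stated for the symptom endpoints. The figure that can be checked is the original sample size for TBUT (SAP 5.3.1: difference 4, SD 5, power 80%). Per arm, n = 2 × (1.960 + 0.842)² × 5² / 4² = 24.5, rounded up to 25, so 50 in total, as stated. This confirms two-sided 0.05 as the design level. The appendix runs (SAP 5.8) use one-sided 0.05 instead; their total of 42 with power 0.817 also reproduces on that basis.

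**Independent tests, both symptom nulls true.**
- At least one significant result in either direction: 1 − 0.95² = 9.75%.
- At least one significant result in favour of IPL: each two-sided test puts 0.025 on that side, so 1 − 0.975² = 4.94%, against 2.5% for one test.

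**Correlated tests.** Let c = 1.960 and let Φ₂(a, b; ρ) be the bivariate normal distribution function, with positive values favouring IPL.
- Either direction: 1 − [Φ₂(c, c; ρ) − 2Φ₂(c, −c; ρ) + Φ₂(−c, −c; ρ)]
- Benefit only: 1 − Φ₂(c, c; ρ)

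The last two columns use half the level per test (c = 2.241), which is the first step of Holm.

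| ρ (assumed) | As planned, either direction | As planned, benefit | Half level, either direction | Half level, benefit |
|---|---|---|---|---|
| 0 | 9.75% | 4.94% | 4.94% | 2.48% |
| 0.5 | 9.07% | 4.54% | 4.65% | 2.32% |
| 0.7 | 8.35% | 4.17% | 4.30% | 2.15% |
| 0.8 | 7.81% | 3.90% | 4.02% | 2.01% |
| 0.9 | 7.04% | 3.52% | 3.62% | 1.81% |

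**What a TBUT gate does alone.** Simulations of 2,000,000 draws took symptom correlations of 0.5 and 0.7, and correlations of 0 to 0.5 between TBUT and each symptom test. If IPL has no effect on TBUT either, the gate cuts the benefit-direction rate from 4.1–4.5% to 0.1–0.8%. If IPL does improve TBUT, the gate is usually open and the rates in the table largely return. A gate therefore needs a second rule, for the two symptom tests themselves.

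**The case against.** The strongest reply is that these are secondary endpoints. Success rests on TBUT only, SAP 4.1.2 says "The following secondary efficiency endpoints will be estimated", and each test has its own stated level. Much of this stands. The primary error rate is untouched. No section says that OSDI or EDS alone, or after a failed TBUT, proves symptom benefit; that rule is an inference from silence. But the plan also writes formal hypotheses, assigns them a significance level and nowhere calls them supportive. If supportive was meant, one sentence would settle it.

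Three stronger readings are tempting and should be resisted.

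- A reader might infer that the chance of a false symptom claim is 8–10%. That figure counts results in which IPL is significantly worse than sham, which nobody would present as symptom benefit. It would be close to the benefit rate only if each test were one-sided at 0.05, as in the appendix power runs, and SAP 5.7 rules that out. Even as an either-direction rate it falls to 7.8% at correlation 0.8 and 7.0% at 0.9.
- A reader might say that the symptom endpoints have no error control. Each test is held at 0.05; what is missing is control across the pair.
- A reader might add that subjects who report their own symptoms cannot be reliably masked (SAP 2.7). That is a source of bias. No testing order creates it or removes it, and it does not strengthen the multiplicity argument.

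A further objection limits the numbers. SAP 5.7 names a paired t-test for OSDI, which tests change within subjects and not the between-arm hypothesis of SAP 5.2. It also treats EDS as one value per eye, while Protocol 5.1.5 describes a single score for both eyes. Until these separate problems are corrected, the text does not fix the actual error rates.

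**Conclusion.** The gap is real and modest. Across correlations 0 to 0.8, the chance of at least one false claim of symptom benefit is 3.9–4.9%, about 1.6 to 2 times the 2.5% of a single test, or 1.4 to 2.4 percentage points more. In either direction it is 7.8–9.8% against 5%. These rates assume that both symptom nulls are true, that each test is a valid between-arm test at two-sided 0.05, and that the correlation lies in the assumed range.

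The TBUT conclusion is not at risk. What is affected is the strength of any symptom claim, and the change is worth making because it needs only wording.

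**What to change.** Add to SAP 5.7, before unmasking:

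1. OSDI and EDS are tested for significance only if the primary TBUT criterion is met. Say which TBUT analysis opens the gate, because SAP 5.7.1 can split it into A1 and A2+B+C without saying which result counts.
2. If the gate opens, use one of two rules. Either apply Holm across OSDI and EDS at an overall two-sided 0.05, which needs no ranking, or test them in one fixed order, each at two-sided 0.05, going on to the second only if the first is significant in favour of IPL. The documents do not settle the order, so the sponsor must choose it.
3. Each step is a between-arm comparison of change. The paired t-test must not serve as the OSDI step.
4. In all other cases report estimates and 95% confidence intervals without a significance claim. Exploratory and safety p-values are descriptive.

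Make the list orders in SAP 2.3, 4.1.2 and 5.2 and in Protocol 6.1.2 consistent, and carry the rule into Protocol 7.4 if it is amended.

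**Cost.** There is no loss of power for TBUT. If TBUT fails, both symptom endpoints become descriptive; the design accepts a 20% chance of this even under its assumed effect. If TBUT succeeds, the fixed order leaves the second endpoint descriptive whenever the first fails, and Holm costs a little power because the smaller p-value must first pass 0.025.

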5.7.1. Stratified Analysis

To account for the potential loss of IPL treatment effect at one site (hereafter called "A") a stratified analysis will be performed that includes a separate stratum comprising subjects at site A who were treated prior to the corrective action. The strata will be labeled as A1, A2, B, and C for sites A, B, and C, with A1 and A2 the two separate groups of patients at site A before and after the corrective action. Since the treatment is applied over a sequence of four visits, we will conservatively assign to stratum A2 only those patients who received all four of their treatments subsequent to the corrective action. Any patient who received any one of their four scheduled treatments prior to the corrective action will be assigned to stratum A1.

Stratum	Corrective Action	Description
A1	No	Patients from site A with one or more treatment visits prior to the corrective action

Thus, the following four strata are obtained:

A2	Yes	Patients from site A with all 4 treatment visits subsequent to the corrective action
В	No	Patients from site B
C	No	Patients from site C

An ANOVA analysis will be performed for the change in TBUT primary endpoint, with fixed effects for treatment and stratum and a random subject effect.

To examine the effect of the corrective action, we will group the strata into two sets: {A1}, for the pre-corrective-action subjects at site A, and {A2+B+C} for all post-corrective-action subjects at site A, combined with all subjects at B or C. We will test for significance of the corrective action by creating a 1 degree of freedom contrast for "treatment by corrective action", using treatment (1 df) and the two corrective action sets (1 df), and test whether the contrast is significantly different from 0, using a two-sided alpha of 0.15.

- If the contrast is not significant, then the results will be analyzed as planned, pooling across all strata pre- and post- corrective action.
- If the contrast is significant then we will carry out the analyses separately for A1 and for the combined {A2+B+C}.

We will also directly compare outcomes between A1 and A2 by calculating the LSM for the difference between the two, along with the associated 95% CI.

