3.3. Analysis Populations

The per-protocol analysis population includes all subjects who have at least one follow-up visit and have no major protocol deviations. The primary and secondary endpoint analysis will be performed based on the per-protocol population.

The intent-to-treat (ITT) analysis population includes all subjects who are randomized to either arm, regardless of treatment received.

4. Study Evaluations

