5.7.2. Analysis Model

The linear mixed effects model for TBUT can be written as follows:

$$y_{ij} = \beta_0 + \beta_1 T_i + \beta_2 TBUT_{ij,0} + b_{0i} + \epsilon_{ij}$$

Where

- $TBUT_{ij,k}$ is the TBUT value for subject i, eye j, week k.
- y_{ij} is the 1 month change from baseline TBUT for subject i, eye j. $y_{ij} = TBUT_{ij,4} - TBUT_{ij,0}$
- T_i is the binary treatment indicator for subject i (0 = Control, 1 = IPL Laser)
- $\beta_0, \beta_1, and \beta_2$ are the fixed effect parameters:
 - \circ β_0 is the mean change from baseline for the Control arm,
 - β_1 is the difference between IPL and Control in mean change from baseline,
 - \circ β_2 is the effect of each unit change in baseline TBUT.

- b_{0i} is the random effect (random intercept term) for subject i $b_{0i} \sim N(0, \sigma_a^2)$
- ϵ_{ii} is the normally-distributed error term ٠ $\epsilon_{ij} \sim N(0, \sigma_e^2)$
- $\{b_{0i}\}$ and $\{\epsilon_{ii}\}$ are independent

The linear mixed effects models can be fit in SAS or R as follows:

In SAS:

Proc Mixed data=IPLdat method=ml; class SUBJ TRT; model TBUT_DIFF = TRT TBUT_BL / solution; random intercept / subject=SUBJ;

In R:

Library(Ime4) fit.tbut <- Imer(TBUT.DIFF ~ TRT + TBUT.BL + (1|SUBJ), REML=FALSE, data=IPLdat)

Note that since we are interested in testing the fixed effects, ML (maximum likelihood) versus REML (residual maximum likelihood) estimates are being used.

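### Pooling of the primary TBUT analysis depends on a contrast tested at 0.15, and the success criterion does not say which result decides after a split

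*SAP*

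**What the plan says.** SAP 5.7.1 and Protocol 7.4.1 divide the subjects into A1 (site A, at least one treatment before the corrective action), A2 (site A, all four treatments after it), B and C. To examine the corrective action, a one-degree-of-freedom contrast compares the treatment effect in A1 with that in {A2+B+C}. The instruction is to "test whether the contrast is significantly different from 0, using a two-sided alpha of 0.15". If it is not significant, "the results will be analyzed as planned, pooling across all strata pre- and post- corrective action". If it is: "If the contrast is significant then we will carry out the analyses separately for A1 and for the combined {A2+B+C".

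Success is defined elsewhere, without reference to strata or to the contrast. SAP 2.2 and Protocol 3.5.2 state: "The study will be determined as successful if it satisfies two conditions". SAP 4.1.1 and Protocol 6.1.1 state: "The success criterion will include the following two conditions". In each place the conditions are one two-sided p-value below 0.05 for study-arm against control-arm eyes, and a larger change in the study arm.

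On alpha, SAP 5.7 says "The level of statistical significance (type I error) is" 0.05, with no allocation between parts. The SAP 5.7.2 model, "model TBUT_DIFF = TRT TBUT_BL / solution", has no stratum term.

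On population, SAP 3.3 bases the primary analysis on the per-protocol set, which "includes all subjects who have at least one follow-up visit and have no major protocol deviations". SAP 5.3.2 sized the trial for an ITT analysis that keeps the mistreated IPL subjects.

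**The concern.** The contrast and the tests that follow it use the same data. If the contrast chooses the analysis, the test that finally decides is selected by the results, and its error rate need not be the nominal one. After a split there are two p-values and a success criterion written for one. Success could be read from {A2+B+C}, from both parts, from either part, or still from the pooled test. Unless the plan chooses, the choice can be made with the results in view.

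The population question is tied to this. The rule needs A1 in the analysis set. SAP 5.3 reports that the lightguide was misplaced for both IPL and sham subjects at that site. If this counts as a major deviation, the per-protocol set loses A1 and the contrast cannot be estimated there.

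**Working it through.** **Inputs from the documents.** Change in TBUT 5±5 s (IPL) and 1±5 s (control), 1:1 allocation, two-sided alpha 0.05, eye correlation 0.5, 8 initial IPL subjects at site A responding like control (SAP 5.3.1, 5.3.2); 83 evaluable subjects (synopsis); contrast at two-sided 0.15 (SAP 5.7.1).

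**Assumptions.** The documents give neither the sham count nor the final IPL count in A1. I take A1 as 8+8, 10+10 or 12+12 (IPL + sham), fully included, with arms of 42 and 41. Tests are t-tests on each subject's two-eye mean, standing in for the SAP 5.7.2 mixed model; baseline TBUT is not used. Success means two-sided p < 0.05 with IPL larger, so the nominal false-success rate is 2.5%. Each setting had at least 100,000 simulated trials.

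**Reproducing the plan.**
- Original size per arm: 2 × (1.960 + 0.842)² × 5² / 4² = 24.5, so 25 per arm and 50 in total, as stated.
- SD of a two-eye mean: √(25 × (1 + 0.5) / 2) = 4.33.
- Adjusted size: 68 subjects, 8 IPL non-responders, pooled test. Simulated power is 0.80, matching the plan's target.

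**How often the split occurs in the plan's scenario (A1 8+8, 83 subjects).**
- Contrast SE = 4.33 × √(1/8 + 1/8 + 1/34 + 1/33) = 2.41.
- True contrast is 4 s; 4 / 2.41 = 1.66.
- The critical value at two-sided 0.15 on 83 − 4 = 79 df is 1.45, so the chance of a split is about Φ(1.66 − 1.45) = 0.58. The simulation agrees.

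**No effect anywhere: false IPL success, by what decides after a split.**

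| A1 | {A2+B+C} | both must win | either counts | always pooled |
|---|---|---|---|---|
| 8+8 | 3.0% | 2.2% | 5.0% | 2.5% |
| 10+10 | 3.1% | 2.1% | 5.1% | 2.5% |
| 12+12 | 3.2% | 2.2% | 5.1% | 2.5% |

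Repeat runs put the {A2+B+C} column between 2.9% and 3.3%. The split itself occurs in 15% of null trials.

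**Plan's scenario: 8 IPL non-responders, 4 s for every other IPL subject.**

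| A1 | split | {A2+B+C} decides | both must win | always pooled |
|---|---|---|---|---|
| 8+8 | 58% | 0.956 | 0.38 | 0.91 |
| 10+10 | 49% | 0.948 | 0.46 | 0.91 |
| 12+12 | 43% | 0.943 | 0.53 | 0.91 |

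Pooled power does not move, because it depends on the number of non-responders and not on the size of A1. A larger A1 with 8 non-responders has a smaller true contrast (4 × 8/10 = 3.2 s, then 4 × 8/12 = 2.67 s), so it splits less often. Always pooling costs 0.956 − 0.91, about 5 points, at 8+8, and about 3 points at 12+12.

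**A harsher assumption than the plan's.** If all 10 or all 12 IPL subjects in A1 fail to respond, pooled power is 0.87 or 0.82.

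**The case against.** The strongest reply is that the stratified analysis was only ever supportive. The success criterion ignores strata, the SAP 5.7.2 model has no stratum term, the sizing assumed one pooled ITT test, and the contrast is introduced as a way to examine the corrective action. On that reading the pooled test always decides and the error stays at 2.5%. The reading is possible, but the text does not adopt it: pooling as planned is stated only for the non-significant branch, and the other branch puts two analyses in its place. The ITT statement is a sizing assumption, and SAP 3.3 contradicts it.

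A second reply is that the alarming figures come from unlikely readings. This largely stands. A reader might infer that false-positive risk is doubled. That needs a win in A1 alone to count as trial success; about 2 of the 2.5 excess points come from that event, and nothing in the documents proposes it. A reader might also infer that the trial could have only a 0.38 chance of success. That needs the cohort suspected of ineffective treatment to win as well.

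Third, a reader might take pooled power of 0.82 as the plan's own adverse case. It is not: SAP 5.3.2 fixes 8 non-responders. A1 may hold more than 8 IPL subjects, since one early treatment is enough for membership, but zero effect is least supported for those partly affected subjects. A split is more likely than not at 8+8, but not at 10+10 or 12+12.

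**Conclusion.** The concern holds as a gap in the primary decision rule, and it should be fixed. Followed as written, with {A2+B+C} deciding after a split, the pre-test lifts favourable-direction error from 2.5% to about 3.0 to 3.3%. That is modest. Of more consequence, the plan does not name the deciding result in a branch reached in about 43 to 58% of trials under its own sizing scenario, and there the overall chance of success depends on the reading taken: 0.96, 0.91 or 0.38 at A1 8+8. {A2+B+C} and pooling both exceed the 80% design target, so this is not a finding that the trial is underpowered.

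The sizes rest on the assumed A1 counts, on A1 being fully included, and on t-tests on subject means in place of the mixed model. If A1 is excluded as a major deviation, these figures do not apply and the contrast has no A1 subjects to use. The missing decision rule does not depend on any of these assumptions.

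**What to change.** In SAP 5.7.1 and Protocol 7.4.1, name one confirmatory test that does not depend on the contrast. Default wording, matching the sizing basis in SAP 5.3.2:

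> The success criterion is judged only on the treatment effect from the model in SAP 5.7.2, pooled over A1, A2, B and C in the ITT population, at two-sided alpha 0.05, whatever the contrast shows. The treatment-by-corrective-action contrast and the separate A1 and {A2+B+C} estimates are reported with 95% confidence intervals as supportive.

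Naming the SAP 5.7.2 model also settles whether it or the ANOVA with stratum effects in SAP 5.7.1 carries the decision.

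In the same edit, reconcile SAP 3.3 with SAP 5.3.2: make ITT the primary population with per-protocol supportive, state that A1 subjects are kept, and give a rule for randomised subjects without a follow-up TBUT (for example, the mixed model on available eyes, with a sensitivity analysis for the missing ones).

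If the sponsor prefers {A2+B+C}, it must be fixed in advance as the sole confirmatory set. No alpha adjustment is then needed, but the claim excludes A1. At A1 8+8 its power is 0.961 in the plan's scenario (pooled 0.91), and also 0.961 if A1 responds fully (pooled 0.986).

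Cost: amended text in both documents, a change of primary population, and a missing-data rule to write. Against letting {A2+B+C} decide after a split, always pooling gives up about 3 to 5 points of power in the plan's scenario, leaving about 0.91.
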